
Sample size/ Power calculations

Power calculations are based on our primary analysis, which is to assess the effect of each intervention component (e.g., shorter counseling vs. longer counseling) on our primary outcome, 7-day point-prevalence tobacco abstinence at 6-month follow-up. This is a two-sample comparison between patients that receive one intervention component (e.g., longer counseling) and those that receive the other (e.g., shorter counseling). We conservatively estimate that 160 patients/month will have LCS, of whom 50% will be current smokers. Assuming a 50% enrollment rate, we aim to recruit a total N of 720 patients. This sample size allows us to allocate N=360 to each treatment component comparison (main effect). Our

Reference rate	Relative Risk		
	1.4	1.45	1.5
16%	0.71	0.80	0.87
17%	0.74	0.83	0.90
18%	0.77	0.86	0.92
19%	0.80	0.88	0.93
20%	0.83	0.90	0.95
21%	0.85	0.92	0.96
22%	0.87	0.93	0.97

outcome of interest will also be assessed at 3-month followup, which allows us to use a longitudinal generalized estimating equations approach wherein power is proportional to the within-person correlation. We estimate the correlation between 3 month and 6 month smoking cessation to be 0.6. Assuming N=360 patients in each condition, a Type 1 error rate of 0.05, a 25% attrition rate by 6 month follow-up, and a 15% cessation rate for the reference group, we will have 92.3% power to detect a risk ratio of 1.6 (15% vs. 21%). Under those same conditions, but with a 10% cessation rate for the reference group, we will have 79.0% power to detect a risk ratio of 1.6 (10% vs. 16%). Given that this is full factorial design, we will have the same power to detect two-way interactions between components. Further, we will also have 77.9% power to detect a risk ratio of 2.0 in the difference between our most intensive set of treatments (longer counseling, longer NRT, and community support; N=90) and our least intensive set of treatments (shorter counseling, shorter NRT, and no community support; N=90) after six months, assuming a 15% reference rate and 25% attrition.

Reduction from initial power calculations

This study was initially powered conservatively to detect a smaller risk ratio of 1.4 and did not account for additional power provided through within-person correlation via repeated measurement of our outcome of interest. Initial power calculations, assuming a Type 1 error rate of 0.05, 25% attrition at 6 months, and no within-person correlation showed that our original N of 960 patients (N=480 per condition) gave us 85.0% power to detect a risk ratio of 1.4 with a reference rate of 15%. Updated power calculations accounting for within-person correlation of 0.6 show that this original N gives us 96.8% power to detect our target risk ratio of 1.6, assuming 25% attrition at 6 months and a 15% reference cessation rate.

Our previous power calculation assumed a 25% attrition rate at 6 months. We re-examined this assumption after halfway through the recruitment. Our new estimates are 12.7% attrition rate at 3 months and 15.9% attrition rate at 6 months. Based on these estimates, we further reduce the target recruitment from 720 to 640. Combining data from both 3-month (estimated N=559) and 6-month (estimated N=539) assessments, the effective sample size will be 768 after taking into account of within-person correlation using a conservative estimate of 0.6. The new sample size will have 70% power to detect a risk ratio of 1.6 (10% vs. 16%) and 81% power to detect a risk ratio of 1.7 (10% vs. 17%).

VII.. RISKS AND DISCOMFORTS (Stratify by common and uncommon)

Prior to enrollment, potential patients will be cautioned about the potential negative psychological and physical implications of joining the study and/or quitting smoking.

Psychological Risks

Individuals may find it stressful to answer questions and discuss their smoking behaviors. The risks associated with these discussions are minimal, especially when compared to the benefits of smoking cessation.

The potential risks to subjects include: 1) speaking with a counselor about smoking and/or cancer-related topics has the potential for increasing psychological vulnerability; 2) experiencing physical and emotional withdrawal symptoms from smoking cessation; and 3) potential side effects of using nicotine replacement therapy.

These risks will be described by the research assistant and will be clearly outlined in the consent script. Among enrolled patients, in the event that a patient is determined to be actively suicidal and at risk for self-harm at any of the study contact points, the study PIs will be immediately contacted and the appropriate clinical intervention effected. These procedures would be followed in the case of active suicidality or homicidality, as well as in the case of abuse, neglect or risk of harm to a minor or elder.

Toxicities and Side Effects

Nicotine Replacement Therapy (Nicotine Patch)

The transdermal nicotine patch has been an FDA-approved treatment for nicotine dependence since 1991, and in 1996, the patch was approved for over-the-counter sale. Up to 50% of patients using the nicotine patch will have a local skin reaction. Skin reactions are usually mild and self-limiting but may worsen over the course of therapy. Local treatment with hydrocortisone cream (1%) or triamcinolone cream (0.5%) and rotating patch sites may ameliorate such local reactions. In less than 5% of patients, such reactions require the discontinuation of nicotine patch treatment.

Nicotine is not an independent risk factor for acute myocardial events, but NRT should be used with caution among those in the immediate (within 2 weeks) postmyocardial infarction period, those with serious arrhythmias, and those with serious or worsening angina pectoris. Mild sleep disturbances, such as vivid dreaming or insomnia, have been reported for approximately 12% of patients wearing the transdermal nicotine patch for 24 hours.⁹⁸ Other less common side effects are nausea, dizziness, tachycardia, upset stomach, restlessness, and headaches.

As our patient population may have existing physical and psychological symptoms, we will make every effort to determine if any symptom reported has its onset concurrent with or is exacerbated by medication use. In cases of severe or intolerable symptoms, patients will be instructed to discontinue use of the study medication and to contact their physician.

VIII. POTENTIAL BENEFITS

There are substantial benefits for individual subjects participating in this research study. Quitting smoking reduces risk of developing cancer, as well as improving cancer treatment effectiveness for patients diagnosed during the LCS, reducing risk of recurrence and of developing new primary tumors, and may improve chances of survival. Conversely, continuing to smoke may result in diminished quality of life (e.g., elevated pain, shortness of breath). If they succeed in quitting, the greatest potential benefit is improved outcomes and quality of life (e.g. increased breathing capacity). The potential short-term (e.g. improved breathing) and long-term (e.g. improved treatment outcome) health benefits of this study are tremendous. In addition, all patients will receive counseling during a potentially difficult time, which can bolster their sense of support and self-efficacy. Patients will receive support and counseling that may assist them with medication adherence and increased rates of tobacco cessation and continued abstinence. Patients may receive access to community resource database to address sociocultural barriers to cessation. Therefore, the overall risk to benefit ratio is favorable.

IX. Data and Safety Monitoring (DSM) Plan

The PIs will be responsible for monitoring the safety and effectiveness of this trial, executing the DSM plan, and complying with reporting requirements. The final protocol will be reviewed by the Partners IRB. The PIs will supply a summary of the DSM report to the NIH on an annual basis as part of the progress report. This report will include descriptive reports of the patients' sociodemographic characteristics, expected and actual recruitment rates, retention rates in each treatment condition, quality assurance, and regulatory issues that arose since the last report, summary of adverse events and serious adverse events, and any protocol changes. This report will include the results of any effectiveness data analyses conducted. Throughout the study, adverse events and serious adverse events will be reported in a timely fashion to the IRB. The PIs are responsible for protecting the rights, safety, and welfare of the study patients and for ensuring that the study is conducted in accordance with the IRB-approved protocol and applicable regulations and requirements of the IRB.

Data monitoring plan: Study procedures and data collection will be piloted before the trial begins. Participant data collected using paper and pencil records (participant questionnaires, progress notes from smoking cessation counselors) will be stored in a locked filing cabinet in a locked room; electronic participant tracking databases will be stored on a secure server accessible only by IRB-approved members of study staff. Data collected on paper and pencil forms will be thoroughly cleaned and entered into an electronic database with a 10% check; discrepancies will be resolved by the investigator team through a monthly data review meeting. Data collected using REDCap will identify patients by their names, email address, date of birth, medical record number, and by study ID. Participants will be identified on study forms and in the database by their names, email address, date of birth, medical record number, and by study ID. To further prevent the loss of confidentiality, all electronic information stored on the main database within the MGH/Partners Healthcare System, Inc. firewall, is password protected, and is protected by anti-virus software. Only study staff will have access to the study data on Shared File Areas. [name] will review the data for quality assurance and discuss data quality problems with the PIs. Data quality (including visits completed during the intervention window, data missingness, and recruitment rates) will be monitored monthly. Interim data analysis will be conducted throughout the trial and results will be reported in the annual NIH progress report. In addition, the RAs will participate in weekly study evaluation meetings to review any difficulties that arise with survey administration and the status of follow-up survey and biochemical collection.

If patients report significant complaints about our recruitment approach, the study RA will document all patient concerns and provide a detailed report to the IRB in real time about the nature of the complaint. Study staff will discuss with the PIs on how to adapt recruitment approaches to prevent future complaints, and include any changes required by the IRB.

Safety monitoring plan: The exclusion criteria are designed to prevent patients at a high risk of medical and psychiatric complications from participating in study. However, if unexpected conditions appear to be placing patients at a higher risk than anticipated, the exclusion criteria will be amended. Any medical complications, which are considered to be related to the study, will be reported to the site PI, who will report them to the subject's treating physician. The site PI will review the progress of all study participants on an at least monthly basis. Any adverse events related to study participation will be reported to the IRB.

The main safety risks for the study include the potential for psychological discomfort with

surveys and counseling as well as side effects from study medications. In order to protect against risk from pharmacotherapy usage, these steps will be taken:

- (1) Medication is being provided only to patients who receive counseling sessions. At each call, patients are specifically asked about any side effects or problems. Study staff will be required to report any unexpected or questionable reports of adverse effects to the study PIs. These will be reviewed at the weekly study staff meeting. If more urgent, the PI will review immediately.
- (2) The study physicians (Drs. [name] and [name]) will provide back up to study staff for all medical questions that arise during participant enrollment or study progress.
- (3) The PIs will review any serious adverse events and report them appropriately to the IRB and NIH. Reports are to be submitted within 5 working days/7 calendar days of the date the investigator first becomes aware of the problem. Each will be reviewed by the PIs to ensure that the readmission is not related to study medication.

Data Sharing

De-identified data will be periodically shared with NCI for cross-project research within the SCALE study sites. Data will be shared through a secure online portal developed by Information Management Services, Inc. (IMS), in which each SCALE study site will only have access to the data uploaded by members of that site. IMS provides a firewall, VPN, and intrusion prevention system. Routine security checks of the IMS computer resources are made with security analysis software tools. The production network is housed in physically separate and secured computing facilities. Only authorized user ID and password protected access is allowed to the network. In addition, IMS has an NIH approved IT System Security Plan in place that meets the OMB Circular A-130 guidelines and the NIST guidelines for IT system security at the “moderate” level.
As part of the SCALE collaboration, a data transfer agreement written by the NCI legal office will be sent to each study site for review by each site’s legal offices. Research proposals will be sent to the soon-to-be formed Steering Committee (in which NCI is a non-voting member) and vetted. When approved, NCI will send data to the researchers who are leading a given analysis; NCI may also conduct analyses with the approval of the Steering Committee. NCI will only send data to non-SCALE members when approved by the Steering Committee, except in very specific, limited circumstances described in the data transfer agreement.

We will send a limited data set to our collaborator at UMass Boston, [name] [name]. [name] will assist us with the data analysis. Data will be stored behind the UMB firewall on a password protected computer, for added safety the data will be stored in the University OneDrive under a two-way steps verification.

Protection of Human Subjects

Prior to enrollment, potential patients will be cautioned about the potential negative psychological (stress and loss of positive experiences from smoking) and physical implications of quitting smoking. A clear risk/benefit ratio will be presented to each potential patient. These risks will be described by the research assistant and will be clearly outlined in the consent script. Patients will

be encouraged to discuss any concerns with their provider, prior to enrolling. Patients who need time to consider these risks will be given the option of calling back and/or enrolling at a later date.

There are three potential reasons for elevated psychiatric risk in our study patients. Lung cancer screening could be a vulnerable time for patients, patients may be uncomfortable talking about their smoking given the stigma of smoking and lung cancer, and withdrawal symptoms and cravings from quitting smoking.

In order to protect against psychiatric risks, we will not enroll anyone who is potentially psychiatrically unstable. Individuals found to be psychiatrically unstable at screening will be referred for psychological/psychiatric evaluation. Once patients are enrolled in the study, study staff will notify the MPIs if a patient seems distressed during the surveys or counseling. In addition, patients will be given the contact information for the study MPIs at the beginning of the study and told that they can contact with any concerns about their study participation. If a patient appears to be in high distress/risk the tobacco counselor will page [name], who will immediately contact the patient and utilize a suicide prevention assessment and protocol previously developed for smoking cessation studies with other vulnerable medical patient populations. This protocol assesses for risk to self or others, including whether the patient has suicidal thoughts, a suicide plan, and a means to complete their plan. If a patient is deemed high risk of suicide/homicide, confidentiality may be suspended. Patients in the midst of a psychiatric emergency will be required to go to the emergency room for evaluation (if they are unwilling, paramedics will be sent to their location). Suicidal patients who are able to contract for safety will be required to follow up immediately

The study staff will immediately discuss any patients whom they are concerned about with the Drs. [name] or [name], both licensed internists, who will decide an appropriate course of action. In the event of a psychiatric emergency, confidentiality may be suspended. Patients will be informed of the limits of confidentiality at the beginning of the study.

X. REFERENCES

2. American Cancer Society. Cancer Facts & Figures. Atlanta; 2016. doi:10.3322/caac.20121.
3. [name] NA. Clinical practice. Treatment of tobacco use and dependence. *New England Journal of Medicine*. 2002;346(7):506-512.

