expressed the need for time and repeated offers to engage in a cessation program. Given these barriers, it is imperative to offer cessation treatment at multiple points of LCS delivery. We propose that the LCS process provide 3 systems-based patient-engagement opportunities that 1) integrate into the screening process, 2) include primary care and radiology, and 3) use a population health management perspective.

II. SPECIFIC AIMS (Research Objectives)

Aim 1: To develop a centralized smoking cessation treatment (care coordination and intervention components) at 10 MGB LDCT-LCS screening sites.

Aim 2: To test the effectiveness of the intervention for smoking cessation in a randomized controlled trial using a factorial design to assess 3 intervention components:

- (a) Duration of counseling contact (repeated proactive sessions delivered by a trained tobacco treatment specialist using phone or videoconferencing telehealth platform);
- (b) Duration of NRT, and
- (c) Referral to community-based resources to address social barriers.

Aim 3: To evaluate the reach, adoption, implementation, and maintenance of the intervention. The components of the LCS-tailored intervention are informed by our preliminary studies and conceptual frameworks.

III. SUBJECT SELECTION

Patients: Inclusion and exclusion criteria. Patients who are scheduled to undergo LDCT-LCS at a participating PHS LCS site, speak English or Spanish, and are current smokers are eligible. Current smokers will be defined as those who have smoked a cigarette, even a puff, in the last 30 days. Smokers will fulfill the Medicare coverage requirement (age 50-80 years, 20+ pack/years). Smokers do not have to be ready to quit smoking. We will exclude patients who are: (1) undergoing lung CT as part of a diagnostic or abnormal follow-up evaluation, (2) unable to give informed consent due to psychiatric or cognitive impairment as determined in consultation with study PI or treating clinician, (3) who do not have access to a telephone or cannot communicate by telephone, or (4) do not reside within the United States of America.

IV. SUBJECT ENROLLMENT

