Recruitment Point 3. LDCT Result. After the patient has received the result, patients who have not previously enrolled or refused further contacts will be sent a short video recruitment message tailored to the result via a secure, encrypted email including a secure REDCap survey link, or a letter with a URL to a secure REDCap survey. It will invite them to join the study, and

give brief cessation advice from [name] or [name]. Patients will then be contacted by the RA who will use the same workflow as described for Point 1 (i.e., screen, consent, administer baseline survey). Patients who enrolled at an earlier point will receive a short video embedded in a secure REDCap survey tailored to their test result to address why quitting and study participation remain important.

Hispanic/Latino patients that do not enroll will have MRNs shared with study investigators to be approached for protocol # 2019P002549.

Patients may also be contacted for research purposes from the team in the future.

Recruitment Summary: Our recruitment strategy is designed to require little additional effort at busy radiology sites, but make systematic and repeated recruitment offers to enable us to achieve maximal reach.^{5,50,54,55,56,59} To provide data for our implementation evaluation (Aim 3), we will record the numbers and characteristics of patients who are identified, eligible, and enrolled at each time point. We will document reasons for ineligibility and refusal and document EHR-recorded sociodemographic and biological characteristics, medical history, and cancer history of refusers.

Randomization. Patients will be randomized at the time of enrollment (i.e., completed consent and baseline survey), stratified into 9 randomization strata (3 groups of LCS study sites and 3 recruitment points), to a LCS-tailored intervention treatment arm. The intervention arms will consist of 8 groups of equal proportions, based on a 3-factor fully crossed factorial design to efficiently test components that vary on counseling duration, NRT duration, and provision of systematic referral.

V. STUDY PROCEDURES

Data management. A centralized SQL database will be used for patient identification and recruitment, randomization, patient tracking, and data input. It will interface with all data collection efforts (RAs will enter in REDCap).

Intervention arm components

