The additional survey will assess participants' knowledge about electronic cigarettes, perception of electronic cigarette benefits and risks, willingness to use electronic cigarettes as a substitute for combustible cigarettes and will ask about their willingness to be contacted for future research about switching from cigarettes to electronic cigarettes.

Participants who agree to complete the survey will be provided with the options to complete the survey over the phone with a study team member or to have the survey emailed or texted out to them after a study team member has received their consent. Participants who are eligible for and complete the additional survey will receive a \$30 gift card.

We will aim to have 400 participants complete this survey.

Verification of smoking cessation: Due to COVID-19 and after discussion with the NCI Project officer, we will no longer be sending biochemical verification to patients. Patients who self-report 7-day abstinence at 3 and 6 months follow up will be considered non-smokers. Those who are enrolled prior to his change will continue to be sent biochemical verification and offered a \$20 incentive for each sample.

Biochemical verification of smoking cessation: Patients who self-report 7-day abstinence at 3 and 6 months follow-up will be asked to provide a saliva sample to assay for cotinine. Individuals will be offered a \$20 incentive for each sample.

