Organizational Readiness. Site characteristics and site readiness will be measured at each study site. Employees will undergo local training and then each attending employee will answer the readiness items, identified by the SCALE collaboration. Data will be collected anonymously, and employees will be consented through a waiver of documented informed consent. Responses to these items will be collected at baseline and at the end of the intervention phase of the study.

Research staff may also use a Partners approved text messaging service to contact patients who have agreed to be sent text messages during the consent process. This will be used to maximize outcomes from study videos, follow up surveys, and study reminders.

The Area Deprivation Index (ADI) is a measure for social economical status. We plan on using ADI to control for social and economical factors that are not otherwise reported. We plan on using census.gov to import a csv file of participant addresses which will return the 2020 census block group for those addresses. Names and study details will not be included in the process. By knowing the census block group of an address, we can then link that address to the 2020 ADI score.

VI. BIOSTATISTICAL ANALYSIS

Assessment Plan

Outcomes

Primary smoking outcome: 7-day point-prevalence tobacco abstinence at 6-month follow-up.

Secondary smoking outcomes (1) self-reported 7-day abstinence at 3-, and 6- months follow-up; (2) significant reduction (>50% decrease from baseline in cigarettes/day⁸¹); and (3) >24-hour intentional quit attempt at 3-, and 6-months follow-up.

Measures

Moderators

Sociodemographic and biological characteristics [baseline only]. *EHR*: Sex, age, primary insurance, language preference for sessions and study materials. *Survey*: Race/ethnicity, education level, employment, and religiosity. Medical history [baseline and follow-up]. *EHR*: Comorbid tobacco-related disease, ambulatory visits, alcohol consumption. Screening result. *EHR*: Lung RADS score, results of any diagnostic tests (CT or biopsy). Smoking characteristics [baseline and follow-up]. *Survey*: Current cigarettes/day, number of years smoked, e-cigarette use, past and current use of cessation medication and other tobacco products, 24-hour intentional quit attempt, nicotine dependence (2-item Heaviness of Smoking Index from the Fagerström Test for Nicotine Dependence [FTND] which have predictive validity with the overall FTND^{82, 83}).

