Outcome measures will be assessed at baseline, 3-, and 6-months follow-up. At the outset, we will examine the frequency distributions of all variables. Data from all PHS sites will be pooled for analysis, after confirming there is no significant heterogeneity among sites or adjusting as needed. We will compare the baseline characteristics to assess whether randomization distributed covariates evenly. We will determine whether there is differential dropout in the groups and consider developing probability-of-completion weights to obtain unbiased estimates of treatment effect. The primary analysis will assess the effects of each intervention component in terms of its association with the **primary outcome** (cotinine-confirmed or self report of cessation at 6-months follow-up), **secondary smoking outcomes** and **proximal outcomes/mediators**: (a) short vs long counseling (conditions 1/2/5/6 vs. 3/4/7/8), (b) short vs long NRT (conditions 1/3/5/7 vs conditions 2/4/6/8), and (c) provision of systematic referral or not (conditions 1-4 vs. 5-8). Given the balanced complete factorial design,⁹⁴ each of the three main effect estimates will be based on the full sample size of 640. Cross-sectional analyses will be conducted for outcomes assessed at 3, and 6 months separately. For binary outcomes, chi-square tests will be used to compare the outcomes between groups for each follow-up time. For continuous outcomes two-sample t-tests or Wilcoxon rank sum tests, whichever more appropriate, will be used to compare between groups. A longitudinal analysis using Generalized Estimating Equations (GEE) techniques will also assess the overall impact of each component by including data from all follow-up time points. The secondary analysis will examine the interaction between components, which will provide insight into whether certain combinations of components are most useful. We will test the three-way and two-way interaction terms in the regression models. If there are component interactions, we will determine whether the components are synergistic or antagonistic. Exploratory analyses will examine the moderator effects on treatment effectiveness of the intervention components and groups. Of primary interest are sociodemographic characteristics (sex, race/SES, age), smoking characteristics (quit motivation, nicotine dependence), medical history, LCS-related factors (test results, and point of study entry), delivery modality selected (phone vs. video) and language of participation (English vs. Spanish). We will test the effects of these factors in multivariable logistic regression models to determine their association with the primary and secondary smoking outcomes. We will test for interactions between intervention and these factors to determine whether

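### Patients who last smoked 8 to 30 days ago can enrol already meeting the 7-day abstinence definition, and no planned primary or sensitivity analysis allows for them

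*Combined protocol and SAP*

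**What the plan says.** All places are in the combined protocol and SAP.

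- **Entry (III. Subject Selection):** "Current smokers will be defined as those who have smoked a cigarette, even a puff, in the last 30 days". None of the four exclusions concerns people who have already stopped.
- **Primary outcome (VI, Assessment Plan, Outcomes):** "Primary smoking outcome: 7-day point-prevalence tobacco abstinence at 6-month follow-up".
- **Who counts as abstinent (V, Verification of smoking cessation):** since biochemical verification was dropped, "Patients who self-report 7-day abstinence at 3 and 6 months follow up will be considered non-smokers".
- **Randomisation (IV):** patients are "stratified into 9 randomization strata (3 groups of LCS study sites and 3 recruitment points". Smoking status at entry is not a factor.
- **Primary test (VI, Outcomes/analysis):** "For binary outcomes, chi-square tests will be used to compare the outcomes between groups for each follow-up time". A GEE analysis "will also assess the overall impact of each component by including data from all follow-up time points"; no baseline abstinence term is named.
- **Sensitivity analyses (VI, Analysis plan):** two are named, complete cases and multiple imputation. Both concern missing data.
- **Baseline data:** Outcomes/analysis states "Outcome measures will be assessed at baseline, 3-, and 6-months follow-up". The Measures list itemises cigarettes per day and 24-hour quit attempts at baseline, but no 7-day abstinence item.
- **Secondary outcome:** a fall of more than 50% from baseline in cigarettes per day.
- **Cost (VI):** the cost-per-quit denominator is built on the primary outcome.

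**The concern.** The entry window is longer than the outcome window. A patient whose last cigarette was 8 to 30 days before enrolment is a current smoker under section III and already abstinent under section VI. If still abstinent at 6 months, that patient is counted in the same way as someone who stopped during the trial.

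Two things are at stake.

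1. **Power and effect size.** If the components do less for these patients than for the rest, they raise the abstinence rate at both levels of each component and pull the risk ratio towards 1. The latest power statement is only 70% for a risk ratio of 1.6, so there is little room.
2. **Meaning.** Aim 2 and the cost-per-quit calculation both speak of cessation. The measured quantity is a blend of new quits and maintained abstinence, in proportions that the plan does not report.

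A smaller consequence is that a patient with 0 cigarettes per day at baseline has no defined value for the more-than-50% reduction outcome, and no rule is given.

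**Working it through.** **1. Reproduce the stated power.** From Reduction from initial power calculations: target 640, effective sample size 768 (384 per level of a component), 10% versus 16%, Type I error 0.05, taken as two-sided.

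Power = Φ[(|p₂ − p₁| − 1.96·s₀)/s₁], where s₀ = √(2p̄(1 − p̄)/n) and s₁ = √((p₁(1 − p₁) + p₂(1 − p₂))/n).

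With n = 384, p₁ = 0.10, p₂ = 0.16 and p̄ = 0.13: s₀ = 0.02427 and s₁ = 0.02417, so power = Φ[(0.06 − 0.04757)/0.02417] = Φ(0.514) = 69.6%. The plan says 70%. For 10% versus 17% the formula gives 81.1%; the plan says 81%. Both reproduce.

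The 6-month chi-square alone, with all 640 patients (320 per level) and missing counted as smoking, has 61.7% power for 10% versus 16%.

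**2. Add recent quitters with no component effect.** Let f be the share already 7-day abstinent at entry and q their abstinence rate at 6 months. The documents give neither. I assume f = 2–10% and q = 40–60%, equal at both levels, with 10% versus 16% in the rest. Each level's rate is (1 − f)p + fq.

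| f | q | Rates | RR | Power, n = 384 | Power, n = 320 |
|---|---|---|---|---|---|
| 0 | – | 10.0% vs 16.0% | 1.60 | 69.6% | 61.7% |
| 2% | 40% | 10.6% vs 16.5% | 1.55 | 66.4% | 58.5% |
| 5% | 50% | 12.0% vs 17.7% | 1.475 | 60.3% | 52.7% |
| 10% | 40% | 13.0% vs 18.4% | 1.42 | 53.9% | 46.7% |
| 10% | 60% | 15.0% vs 20.4% | 1.36 | 50.0% | 43.2% |

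The risk difference shrinks only to (1 − f) × 6 points: 5.9, 5.7 and 5.4 at f = 2%, 5% and 10%. Most of the fall in the risk ratio comes from the higher reference rate.

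Recent quitters' share of reference-level abstinence is fq divided by the reference rate: 0.008/0.106 = 8% at the low end and 0.06/0.15 = 40% at the high end.

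**3. Let the components also work in recent quitters** (f = 10%, n = 384).

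- Same risk ratio, 40% versus 64%: reference 0.9 × 0.10 + 0.1 × 0.40 = 13.0%; other level 0.9 × 0.16 + 0.1 × 0.64 = 20.8%. RR = 1.60 and power 82% (75% at n = 320).
- Same absolute gain of 6 points, 50% versus 56%: 14.0% versus 20.0%, RR 1.43, power 60%.
- Same odds ratio (1.71), 50% versus 63.2%: 14.0% versus 20.7%, RR 1.48, power 69%.

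So the direction of the power change depends on how the components act in this group.

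**4. What the analysis changes would do.** In the model of step 2, a test stratified on baseline 7-day abstinence raises power at n = 384 from 66.4% to 66.9% (f = 2%, q = 40%) and from 50.0% to 56.0% (f = 10%, q = 60%): a gain of about 0.5 to 6 points. Restricting to patients who smoked in the last 7 days leaves 384 × (1 − f) per level and gives 69%, 67% and 65% at f = 2%, 5% and 10%.

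**The case against.** The strongest reply is that dilution is not shown. A reader might infer from the mismatch that the component effects are diluted. The documents do not support that. The outcome is judged at 6 months, so a recent quitter succeeds only by staying abstinent; those who relapse or are lost count as smokers. The background section motivates the components as sustained treatment of a chronic condition, so longer counselling or NRT could act by preventing relapse. Step 3 shows that an equal risk ratio in this group leaves nothing diluted. This stands. What it does not show is that power is safe in general: full preservation in that example needs a 24-point gain in recent quitters against 6 in everyone else.

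A reader might also infer bias. Randomisation balances the group in expectation, so the comparison is valid and Type I error is unaffected. That stands too.

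The group may be small. Clinicians record current or former smoking when ordering the scan, and the population is described as long-term heavy smokers, many not ready to quit. On the other hand, enrolment can follow the scan or its result, so the recorded status may be out of date, and the 30-day rule decides eligibility. At f = 2% the loss is about 3 to 4 points.

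The planning rates may already include such patients. If both 10% and 16% describe everyone enrolled, the stated power needs no correction. If instead only the 10% does, and the risk ratio of 1.6 applies to the rest alone, the loss is larger: power at effective N 768 runs from 63% (f = 2%, q = 40%) to 18% (f = 10%, q = 60%). The plan does not say which is meant.

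Finally, exploratory moderator models and a baseline comparison are planned. They name quit motivation and nicotine dependence, not abstinence at entry, and do not touch the primary result.

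**Conclusion.** The mismatch is real: the plan admits patients who already meet its 7-day definition, and neither the primary analysis nor a named sensitivity analysis accounts for them. The test remains valid. What is exposed is power, the size of the risk ratio, and the reading of the result as cessation, including in cost per quit. The last of these holds whether or not there is dilution.

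The size cannot be settled from the documents. With 2–10% recent quitters, 40–60% of them abstinent at both levels and 10% versus 16% in the rest, the risk ratio is 1.55–1.36 and power falls from 70% to about 66–50% at effective N 768, or from 62% to 59–43% at 320 per level. With an equal risk ratio in recent quitters (10% of patients, 40% versus 64%), the risk ratio stays at 1.60 and power is 82%. The conclusion is that effects may be diluted, not that they are. It is worth a change because the remedy is cheap and would show whether the group is too small to matter.

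**What to change.** 1. Leave eligibility as it is; a 30-day window suits proactive recruitment that does not require readiness to quit.
2. Confirm that smoking in the past 7 days is captured at baseline. The general statement in Outcomes/analysis implies it; the Measures list does not itemise it. Report the share already abstinent by level of each component.
3. Replace the unadjusted primary chi-square with a model that adjusts for baseline 7-day abstinence, and put the same term in the GEE.
4. Prespecify a sensitivity analysis in patients who smoked in the 7 days before randomisation. Keep it secondary: if the components prevent relapse, restriction discards real information (65% power against 82% in the f = 10% example).
5. Use that same set for the more-than-50% reduction outcome, and state that it is not defined at a baseline of 0 cigarettes per day.
6. Describe the primary result and the cost-per-quit denominator as abstinence at 6 months, with the breakdown by baseline status alongside.

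Cost: SAP wording, a little more analysis, possibly one baseline item, and a smaller sample in the restricted analysis. If the item was not asked of patients already enrolled, baseline cigarettes per day is a partial substitute, and the SAP should say so.
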